Angelman Syndrome Video Assessment (ASVA) Source Material Study CAS-CAS006-01 v2.0

02 May 2022

Principal Investigator:

[name]
[name]
[name]
[contact]
[contact]

Notification of Confidentiality

THIS DOCUMENT INCLUDING ANY ATTACHMENTS IS THE PROPERTY OF CASIMIR, AND FOR THE SOLE USE OF THE INTENDED RECIPIENT(S) AND MAY CONTAIN CONFIDENTIAL AND PRIVILEGED INFORMATION. ANY UNAUTHORIZED REVIEW, USE, COPY, DISCLOSURE, OR DISTRIBUTION IS PROHIBITED.

Table of Contents

1	Sy	ynopsis	3
2	In	ntroduction & Background	4
3	St	tudy Design	5
	3.1	Objectives	5
	3.2	Endpoints	5
	3.3	Measures Taken to Minimize Bias	5
4	Pa	articipants	5
	4.1	Inclusion/Exclusion Criteria	5
	4.2	Recruitment	6
	4.3	Informed Consent	6
	4.4	Eligibility Determination	7
	4.5	Discontinuation Criteria	7
5	St	tudy Procedures	7
	5.1	Schedule of Visits & Assessments	7
	5.2	Description of Remote Visits & Assessments	8
	5.3	Safety Reporting	9
	5.4	Participant Withdrawal	10
	5.5	Compensation	10
	5.6	Study Personnel	10
6	D	Data Management	10
	6.1	Data Storage	10
	6.2	Record Retention	10
	6.3	Confidentiality	10
7	D	Data Analysis	11
8	Et	thical Considerations	11
	8.1	Risks, Stress or Discomfort	11
	8.2	Benefits	11
9	Pι	rublications & Future Use of Data	12
10)	Financial Disclosure	12
1:	1	References	12

1 Synopsis

Study Title:	Angelman Syndrome Video Assessment (ASVA) Source Material Study (SMS)
Protocol ID:	CAS-CAS006-01
Study Design:	This is a longitudinal, observational, nonrandomized, fully remote study enrolling approximately 55 participant-caregiver dyads. The study includes no treatments or interventions, and participants will not be asked to change their current treatments.
Objectives:	The objective of this study is to gather sufficient source material videos to develop a scoring system for ASVA and to perform preliminary validation of that scoring system.
Endpoints:	 ASVA videos collected at baseline, baseline re-test, and again at a 12-week visit. Vineland Adaptive Behavior Scale-Third Edition (VABS-3) scores collected at baseline and again at the 12-week visit. Caregiver Global Impression of Change (CGIC) in each domain at the 12-week visit
Target Population & Sample Size:	40 participants with Angelman Syndrome (AS) and their caregivers (AS-caregiver dyads) and up to 15 neurotypically (NT) developing children and their caregivers (NT-caregiver dyads) for a total of up to 55 participant-caregiver dyads.
Key Inclusion/Exclusion Criteria:	AS-caregiver dyads will be enrolled if the caregiver reports a laboratory confirmed diagnosis of AS, the participating individual with AS is at least 1 years old, and the caregiver is comfortable reading and speaking English. NT-caregiver dyads will be enrolled if the child is between 1 and 8 years old and the caregiver is comfortable reading and speaking English.
Schedule of Assessments:	ASVA videos will be captured 3 times (baseline, baseline re-test, and at a 12-week visit). VABS-3 will be administered 2 times (baseline and at a 12-week visit) as an interview with caregivers. CGIC will be captured in the study app for each of 4 domains at the 12-week visit.
Data Analysis:	Videos will be reviewed and analyzed to develop an ASVA scoring/rating system. Videos captured of neurotypical children will be used as a qualitative comparator to ensure the ASVA scoring system is sufficiently specific to physical and behavioral manifestations of AS. VABS-3 and CGIC data will be used as comparators for validation analyses of ASVA.

2 Introduction & Background

Angelman syndrome (AS) was first described in 1965 as a neurodevelopmental disorder characterized by global developmental delay leading to severe intellectual disability, lack of expressive language, ataxia, tremors, unique behavioral features including a happy predisposition, easy laughter, mouthing of objects, fascination with water, as well as maladaptive behaviors such as hair-pulling and other aggressive behaviors. It was subsequently found to be caused by a lack of expression of the *UBE3A* gene, which may be due to a deletion of the critical segment from the maternally-inherited copy of chromosome 15q11q13 that encompasses *UBE3A* (in about 70 - 75% of affected individuals), a pathogenic variant in the maternally-inherited copy of *UBE3A* (in about 10%), paternal uniparental disomy (UPD) of chromosome 15 (in about 5 - 10%), or an imprinting defect (in about 5 - 10%) Estimates of prevalence are approximately 1 in 20,000 to 1 in $50,000.^{1-3}$

Individuals with AS present with moderate to severe degrees of cognitive deficits and neurological manifestations, with deletion-type AS typically having more severe deficits.⁴ Epilepsy is common.^{5,6} Most individuals with AS use few spoken words, if any, and possess better receptive than expressive communication skills.⁷ AS is also marked by some common physical features (e.g., microcephaly, thin vermilion of upper lip) and a high prevalence of scoliosis. Behaviorally, individuals with AS commonly have a decreased need for sleep or other sleep-related issues, are easily excitable and/or are prone to hyperactivity, and have a happy demeanor.⁵ Developmental delays typically appear within the first year of life.⁵ Life expectancy is near normal, and individuals with AS require functional support throughout their life span.^{1,5} Current treatments for AS are, therefore, generally supportive in nature.⁵

Therapeutic interventions that target the underlying genetic causes of AS are in development. Any therapy aimed at modifying the neural substrates of the disorder may affect multiple functional domains if they result in improved neuronal functioning. To date, outcome measures available for use in therapeutic trials for AS focus on specific, individual functional domains often using in-clinic standardized neurodevelopmental assessments that may be insufficiently sensitive to identify changes in habitual function.

Thus, the Angelman Syndrome Video Assessment (ASVA) is being developed by Casimir, LLC (Casimir) in collaboration with Boston Children's Hospital and Ionis Pharmaceuticals to capture observable behaviors and functioning of individuals with AS while in their typical home environment. ASVA is intended to measure changes in relevant functional domains. Results of a previously conducted feasibility study informed a refined list of activities and improved caregiver instructions for the video capture.

The ASVA Source Material Study will be conducted by Casimir, with full funding provided by Ionis Pharmaceuticals, to perform the next phase of development of the ASVA outcome measure. Videos collected as part of the ASVA Source Material Study will be used to develop the scoring system for ASVA and perform preliminary validation of the newly developed scoring system. Videos for pre-specified activities will be captured for individuals with AS across a range of ages and abilities and for neurotypically developing children. The videos will provide sufficient information to devise a scoring system and ensure that the system is tailored to differentiate AS-specific difficulties from neurotypical development.

3 Study Design

This is a longitudinal, observational, nonrandomized study enrolling up to 40 participants with AS and their caregiver (AS-caregiver dyads) and up to 15 neurotypically (NT) developing children and their caregiver (NT-caregiver dyads) for a total of up to 55 participant-caregiver dyads. ASVA videos will be captured 3 times (baseline, baseline re-test, and at a 12-week visit). Vineland Adaptive Behavior Scale v3 (VABS-3) will be remotely administered 2 times (baseline and 12 weeks) as an interview with the caregiver. The study includes no treatments or interventions, and participants will not be asked to change their current treatments.

The study will be remotely conducted (all visits and captures performed at-home). Participant-caregiver dyads that meet inclusion criteria may be enrolled, regardless of their location of residence.

3.1 Objectives

The objective of this study is to gather sufficient source material videos to develop a scoring system for ASVA and to perform preliminary validation of that scoring system.

3.2 Endpoints

- ASVA videos collected at baseline, baseline re-test, and again at 12-week visit.
- VABS-3 scores collected at baseline and again at 12-week visit.
- Caregiver Global Impression of Change (CGIC) at 12 weeks for physical ability, activities of daily living, communication, and attention/focus.

3.3 Measures Taken to Minimize Bias

As an observational study intended to gather source material for outcome measure development, no randomization or blinding will be employed.

4 Participants

Up to 40 AS-caregiver dyads and up to 15 NT-caregiver dyads will be enrolled.

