5.1.1 Baseline Visit Window

The baseline visit window may span approximately 5 weeks. Caregivers will have approximately 2 weeks to complete the baseline VABS-3. Then, participant-caregiver dyads will have approximately 3 subsequent weeks to complete the Baseline Video capture. Visit windows may be extended at the discretion of the investigator.

5.1.2 12-Week Visit

Approximately 12 weeks after the baseline VABS-3 was administered, the 12-week visit window will open and may span approximately 4 weeks. The 12-week interview will be conducted during the first 2 weeks of the window after which participant-caregiver dyads will have approximately 2 additional weeks to complete the final video capture. Visit windows may be extended at the discretion of the investigator.

The table below summarizes the data to be collected at each visit.

Data to be	Data Captured at Remote Visits^		
Collected/Assessments	Consent Call	Baseline	12 Weeks Visit
Contact Information (PII)	Х		
Demographics & Medical History (PHI)	Х		
ASVA		X*	X**

Data to be	Data Captured at Remote Visits^		
Collected/Assessments	Consent Call	Baseline	12 Weeks Visit
VABS-3		Х	X
CGIC			Х

^{*}Baseline ASVA will be captured twice (test-retest) over a 3-week window.

PII=Personal Identifiable Information; PHI=Protected Health Information; ASVA=Angelman Syndrome Video Assessment; VABS-3 = Vineland Adaptive Behavior Scales v3; CGIC = Caregiver Impression of Change

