5.2.4 Vineland Adaptive Behavior Scales (VABS) 3rd Edition

Vineland Adaptive Behavior Scales (VABS-3)^{8,9} is a validated tool for assessing adaptive functioning in daily living, socialization, communication, and motor skills, as well as maladaptive behaviors through a standardized questionnaire administered to caregivers. At baseline and again at the 12-week visit, trained VABS administrators will conduct the interviews with caregivers by using a secure web-conferencing platform and complete the standardized VABS form. Interviews will last approximately 1.5h and will be recorded.

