6.3 Confidentiality

All ASVA videos will be filmed and submitted through a secure platform, and the application will only be accessible to the caregiver by a unique QR code. Videos submitted and recorded interviews will not be de-identified with facial blurring or voice masking.

Government staff sometimes review studies to make sure they are being conducted safely and legally. The U.S. Food and Drug Administration (FDA), other regulatory authorities, patient advocacy groups, and

the Institutional Review Board (IRB) may review participant study data that may contain identifying information.

The following research collaborators will be provided access to identifiable study data using secure and HIPAA/GDPR-compliant data sharing methods:

- Clinician Researchers at Boston Children's Hospital
- Research Collaborators who have signed a confidentiality agreement with Casimir

In the event of breach of electronic data storage for personally identifiable information (PII) or protected health information (PHI), participants and/or caregivers will be notified per Casimir SOP for Handling PHI and/or Identifiable Information (CAS-SOP-063).

7 Data Analysis

This study is intended to capture source material for the development of a scoring system for the activity videos. The videos will be qualitatively reviewed by Casimir and its collaborators to identify quantifiable aspects of behavior that can be included in the scoring system. Once the draft of the scoring system is complete, all videos will be scored using the newly developed scoring system. Subsequently, ASVA and VABS scores will be used to perform preliminary validation analyses for ASVA. The measurement properties for the ASVA scoring system are unknown until after data collection, and, as such, validation analyses cannot be specifically defined *a priori*. Generally, validation analyses will examine the relationships between ASVA domain and activity scores in relation to VABS domain and sub-scale scores. A Statistical Analysis Plan (SAP) will be created at such time as analyses can be specified.

8 Fthical Considerations

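### Section 3.3 rules out all blinding, so the video scoring used to validate ASVA may be done by raters who know the VABS-3 or CGIC results, the time point or earlier scores

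*Protocol*

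**What the plan says.** Protocol section 3.3, Measures Taken to Minimize Bias, contains a single sentence: "As an observational study intended to gather source material for outcome measure development, no randomization or blinding will be employed". It carries no qualification.

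Section 3.1 gives the study two purposes: to collect videos from which a scoring system can be developed, and to carry out a preliminary validation of that system. Section 7, Data Analysis, sets out the sequence. First, "The videos will be qualitatively reviewed by Casimir and its collaborators" to find behaviour that can be scored. Then, "Once the draft of the scoring system is complete, all videos will be scored using the newly developed scoring system". Finally, "Subsequently, ASVA and VABS scores will be used to perform preliminary validation analyses for ASVA". The Synopsis adds CGIC: "VABS-3 and CGIC data will be used as comparators for validation analyses of ASVA".

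Videos come from three occasions. On the first two, the footnote to the schedule table in section 5.1.2 says: "Baseline ASVA will be captured twice (test-retest) over a 3-week window". The third is the 12-week visit.

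No section names the raters, says what they may see, separates them from the developers of the scale or from the VABS-3 interviewers, or sets an order of scoring.

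**The concern.** The reason given in section 3.3 is that the study is observational and gathers source material. That explains why participants and caregivers are not blinded. It does not explain unmasked scoring, which is a separate act of judgement carried out after the videos exist, and whose output is the validation data.

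The risk is criterion contamination. Baseline VABS-3 is completed before video capture (5.1), and ASVA scoring waits until the scoring system has been drafted, so comparator results can exist when the videos are scored. A rater who knows them may score towards them, and the ASVA-VABS correlation then partly measures the rater's knowledge.

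If test-retest agreement is analysed, a rater who remembers or can see the first score may anchor the second to it. If change is analysed, knowledge of the time point or of the CGIC answer may create apparent change. Section 7 names neither analysis, but the re-test and 12-week captures make both likely.

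**Working it through.** **Text check.** The protocol states no power, alpha, effect size or expected correlation, so there is no figure of its own to reproduce. The question is whether any passage limits the sentence in 3.3.

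- Blinding: mentioned in 3.3 and excluded without exception.
- Scoring: section 7 covers all videos, with no rule on raters, masking or order.
- Use of the scores: section 7 relates them to VABS; the Synopsis adds CGIC.
- Opportunity for exposure: section 5.2.4 says of the VABS-3 interviews, "Interviews will last approximately 1.5h and will be recorded"; section 6.3 says, "Videos submitted and recorded interviews will not be de-identified with facial blurring or voice masking", and gives research collaborators access to identifiable study data; section 7 has the sponsor and its collaborators review the videos while building the scale.

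Nothing limits 3.3. Read as written, it allows a rater to know the comparator results, the time point and earlier scores. No passage says that raters will be given them.

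**Size: ASVA against VABS.** All inputs here are assumptions. Let X be the ASVA score an uninformed rater would give and Y the VABS score, both standardised, with true correlation ρ. Suppose the informed rater records X + wY, where w is the shift in SD per SD of VABS. Then

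observed r = (ρ + w) / √(1 + w² + 2wρ).

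For ρ = 0.50 and w = 0.1: 0.60 / √1.11 = 0.569. For w = 0.3: 0.80 / √1.39 = 0.679.

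| True ρ | w = 0.1 | w = 0.2 | w = 0.3 |
|---|---|---|---|
| 0.30 | 0.387 | 0.464 | 0.532 |
| 0.50 | 0.569 | 0.629 | 0.679 |
| 0.70 | 0.746 | 0.783 | 0.814 |

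A simulation of 2 million pairs at ρ = 0.50 gave 0.569, 0.629 and 0.678. An alternative model, in which the rater records the weighted average (1 − w)X + wY, gives 0.577 to 0.731 at ρ = 0.50 over the same range of w, so the table is the more cautious of the two.

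**Comparison with sampling error.** The Fisher-z 95% interval for r = 0.50 is tanh(0.549 ± 1.96/√(n − 3)).

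- n = 40, the maximum number of participants with AS: 0.549 ± 0.322, giving 0.22 to 0.70.
- n = 30, an assumed lower number: 0.549 ± 0.377, giving 0.17 to 0.73.

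At ρ = 0.50 the bias is 0.07 to 0.18. At n = 40 the interval reaches 0.28 below and 0.20 above the estimate, so the bias is the smaller of the two.

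**Size: test-retest, if analysed.** Suppose the second score is recorded as (1 − w) times its own value plus w times the first. Then

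observed r = [(1 − w)ρ + w] / √[(1 − w)² + w² + 2w(1 − w)ρ].

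For ρ = 0.60 and w = 0.1: 0.64 / √0.928 = 0.664. For w = 0.2 it is 0.728, and for w = 0.3 it is 0.789.

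**The case against.** The strongest reply is that the sentence was never about raters. It pairs randomization with blinding and justifies both by the observational design, which is conventional wording about allocation and participants. Section 7 also says that validation analyses cannot be defined in advance and defers them to a SAP, and a scoring system that does not yet exist cannot have a rater manual. On this reading, masking is simply left for later.

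The first part is probably right about intent, and it is also right that exposure is permitted and not shown. Recorded interviews and unblurred faces are privacy statements; they make exposure plausible and prove nothing. The deferral does not settle the matter, however. A protocol that was silent on masking would leave it to the SAP. This one says that there will be none, so a masked-scoring rule written later would contradict section 3.3 as worded.

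It is also fair that the validation is preliminary, that no success threshold depends on the correlation, that the sizes above rest on assumed inputs and suppose that every score is affected, and that test-retest is not named in section 7. These points limit how much weight the figures can bear. They do not turn unmasked scoring into a sound basis for validity evidence on a measure meant to detect change.

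**Conclusion.** The point holds and should be fixed. As written, section 3.3 permits contaminated scoring of the one validation relationship that section 7 names, and it does so under a heading on minimizing bias.

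Under assumed leakage of 0.1 to 0.3 SD per SD, a true ASVA-VABS correlation of 0.50 would be reported as 0.57 to 0.68. If test-retest is analysed, 10 to 30% anchoring would turn 0.60 into 0.66 to 0.79. The bias in the ASVA-VABS correlation is smaller than sampling error at 40 participants, but it always flatters the scale and a larger sample would not reduce it. The conclusion about the text does not depend on these figures. The study remains feasible; what is exposed is the credibility of its validity evidence.

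**What to change.** Limit the sentence in 3.3 to randomization and to the blinding of participants and caregivers. Then add a rule along these lines: *for the scoring used in validation analyses, videos will be coded and presented in random order across participants and time points, and raters will be masked to time point, to earlier scores for that participant, and to VABS-3 and CGIC data.* Operational detail can stay with the SAP or the scoring manual.

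The cost is some file coding and a randomised scoring list, with no extra visit or data capture. Because scoring follows the drafting of the system, masking can still be introduced after the videos have been collected.

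Masking will be imperfect: faces and voices are not obscured, and reviewers who helped to build the system may recognise videos. Comparator results and recorded earlier scores can still be withheld, and that removes the main route of contamination.

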5.1 Schedule of Visits & Assessments

Following informed consent and during the baseline period, caregivers will participate in a remote administration of the Vineland Adaptive Behavior Scales (VABS-3) conducted as an interview. After the Baseline VABS-3, a Training Call will be scheduled by phone or secure web conference to train participating caregivers for video capture and orient them to the study supply kit. After the Training Call, caregivers will capture Baseline ASVA videos, which includes capturing 2 sets of videos (baseline and retest captures). Approximately 12 weeks later, VABS-3 will be remotely administered again, and the participant-caregiver dyad will capture an additional set of ASVA videos and complete CGIC in the study app before exiting the study.

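### Section 3.3 rules out blinding without exception, and nothing keeps the people who score ASVA videos from the VABS-3 and CGIC data used to validate the score

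*Protocol*

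**What the plan says.** Protocol Section 3.3, headed as the measures against bias, consists of one sentence: "As an observational study intended to gather source material for outcome measure development, no randomization or blinding will be employed". It makes no exception for any role.

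The objective in Section 3.1 goes beyond collecting material. The study is also "to perform preliminary validation of that scoring system". The synopsis names the comparators: "VABS-3 and CGIC data will be used as comparators for validation analyses of ASVA".

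Section 7 sets out three steps:

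- **Development.** "The videos will be qualitatively reviewed by Casimir and its collaborators to identify quantifiable aspects of behavior".
- **Scoring.** "Once the draft of the scoring system is complete, all videos will be scored using the newly developed scoring system".
- **Validation.** "Subsequently, ASVA and VABS scores will be used to perform preliminary validation analyses for ASVA". Section 7 names only VABS here; CGIC as a comparator comes from the synopsis.

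Section 7 leaves the detailed analyses to a later SAP, to be written once they can be specified.

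**The concern.** The reason in Section 3.3 is that the study is observational and gathers source material. That explains why there is no treatment blinding, since there is no treatment to blind. It does not explain why the people who score the videos should be free to know the result against which their scores will be validated.

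The relationship between ASVA and VABS scores is the one validation analysis that Section 7 describes. It supports the new measure only if the two scores come from separate sources. If a scorer knows that a caregiver described a child as relatively able on VABS-3, or reported improvement on CGIC, a borderline rating may move in that direction. Part of the agreement then comes from the comparator itself and not from the video. If the people who choose which behaviours to score also know the comparator, the same influence can enter one step earlier.

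**Working it through.** The protocol gives no figure on this point, so there is none to reproduce. The check is a reading of the text, followed by an illustration.

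**1. Does the comparator exist before the videos are scored?** For VABS-3, yes. At baseline the interview comes first: "After the Baseline VABS-3, a Training Call will be scheduled by phone or secure web conference to train participating caregivers for video capture". At the 12-week visit (Section 5.1.2), "The 12-week interview will be conducted during the first 2 weeks of the window", and video capture follows. Section 5.2.4 adds that the interviews are recorded. CGIC differs: Section 5.2.5 places it after the final video capture. It therefore cannot precede filming, but it can be on file when the videos are scored.

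**2. Could scorers or developers reach it?**

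- Section 7 gives development to the company running the study and its collaborators. It does not say who scores.
- Section 5.2.4 requires trained VABS administrators but does not separate them from ASVA work.
- Section 6.3 gives research collaborators access to identifiable study data, with no exception for VABS-3 or CGIC. One of them, the clinical collaborator, is also named in Section 2 as a partner in developing ASVA.
- Section 6.3 also says that neither videos nor interview recordings are de-identified by face blurring or voice masking. Someone who had followed an interview could recognise the family in a video.

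**3. Does any sentence close the gap?** None found. The order in Section 7 (draft, score, then validate) says when the comparison is run. It does not say who may see the comparator beforehand.

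**4. How large could the effect be?** This needs an assumption that is not in the documents. Let A be what the video shows and V the VABS-3 result, both standardised, with true correlation r. Suppose every rating is (1 − w)·A + w·V. Then

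apparent r = [(1 − w)·r + w] / √[(1 − w)² + w² + 2w(1 − w)·r].

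For r = 0.30 and w = 0.10: numerator 0.27 + 0.10 = 0.37; denominator √(0.81 + 0.01 + 0.054) = √0.874 = 0.935; result 0.396.

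| Weight w on known VABS-3 | True r = 0.30 appears as | True r = 0.50 appears as |
|---|---|---|
| 0 (masked) | 0.30 | 0.50 |
| 5% | 0.35 | 0.54 |
| 10% | 0.40 | 0.58 |
| 20% | 0.50 | 0.65 |
| 30% | 0.61 | 0.73 |

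The table shows the direction and how quickly a modest lean adds up. It does not estimate what will happen in this study, and it does not cover influence on the choice of items.

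**The case against.** **Section 3.3 may concern design-level blinding only.** It pairs blinding with randomization in a study without treatments, so this is a natural reading. A reader might infer that the protocol forbids masked scoring, or that scorers will be shown VABS-3. The documents support neither. On the narrower reading Section 3.3 is silent on scorers, and scoring procedures often sit in a scoring manual or SAP. This stands as a limit on the claim. The point remains because the protocol does not leave the matter open: its bias section says no blinding, without exception, and someone who follows it literally may score unmasked.

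**Later repair is possible.** A reader might infer that masking, once lost, could not be restored. That is too strong. The videos are stored (Section 6.1), study data are kept for at least 3 years (Section 6.2), and families who opt in allow use in further validation (Section 9). Scorers without VABS-3 access could rate or re-rate the videos. Section 7 also does not place the SAP after scoring. What would be hard to undo is influence on the choice of items.

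**The illustration should not be pushed.** A reader might infer that a small lean would turn an inconclusive correlation into a positive one. With 40 dyads, the maximum for Angelman syndrome, the Fisher-z 95% interval excludes zero once r reaches about 0.312. Starting from 0.30 (interval −0.01 to 0.56) therefore makes a crossing almost automatic, while at 0.50 the masked interval is already about 0.22 to 0.70. The weight is assumed, and the protocol sets no test against zero and no success threshold, so a crossing corresponds to no decision in the plan.

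**The validation is only preliminary.** True, and Section 9 foresees more. This lowers the stakes but does not remove the reason for a safeguard that costs little.

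**Conclusion.** The point holds as a gap that the plan leaves open. Section 3.3 excludes blinding without exception, for a reason that does not reach scoring, in a study whose objective includes validating the score. No section keeps scorers from VABS-3 scores, interview recordings or CGIC. The likely direction of any bias is a stronger apparent ASVA-VABS relationship; its size cannot be derived from the documents.

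The conclusion rests on reading Section 3.3 as written. It does not assume that scorers will in fact see the comparator. The case is firmest for those who score and weaker for those who draft the scoring system, since the protocol does not say that the score must be built without clinical information. It is also firmer for VABS-3, named in Section 7, than for CGIC, named as a comparator only in the synopsis. This is a cheap improvement worth making before scoring starts, not a flaw that invalidates the study.

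**What to change.** 1. In Section 3.3, limit the statement to randomization and treatment blinding.
2. In Sections 3.3 and 7, state that those who score the videos have no access to VABS-3 scores, interview recordings or CGIC answers until scoring is complete.
3. In Section 7, state that the scoring manual is locked before ASVA scores are linked to VABS-3 or CGIC.
4. Where feasible, apply the restriction in item 2 to those who draft the scoring system.

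This adds no participants, visits, assessments or readers. The cost is access limits on the VABS-3 and CGIC files and recordings, including an exception to the collaborator access in Section 6.3, and keeping VABS-3 administrators apart from ASVA scoring. In a small team that separation takes some effort, which is why item 4 is conditional.
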